5.3 Primary Efficacy Analysis

Change in QALYs from baseline through 18 months post-randomization will serve as the primary outcome for this trial. QALYs were chosen as the primary outcome to facilitate comparisons of the effect of depression screening with other preventive interventions as well as to facilitate cost-effectiveness analyses and policy decisions. As QALYs do not directly assess depression, this outcome measure also minimized possible patient reporting bias as a result of lack of participant blinding or masking to condition. The goal of the primary analysis is to identify whether there is difference in the change in QALYs among the three groups. QALYs describe the duration of illness per years of survival, adjusted for quality of life experienced during that survival. One year in perfect health is equivalent to 1 QALY. All patients will complete a standardized measure of quality of life using the Short Form-12 Health Survey, Version 2™ (SF-12) at baseline, and again at 6-months, 12-months, and 18-months. 1 QALYs will be estimated from the SF-12 using the Short Form 6 Duration (SF6D) which converts data from 7 items in the SF-12 assessing 6 domains (physical functioning, role limitations, social functioning, pain, mental health and vitality) to QALYs.2 Study patients who die during the study period will be assigned a utility score of 0 for assessments after the date of death. QALYs over 18 months will be calculated as the area-under-curve by interpolating linearly the scores at the four assessments (baseline, 6-month, 12-month, 18-month). There were no data obtained or available for these measures between assessments. Change in QALYs will then be obtained by subtracting the QALYs that would have occurred if there was no change in the baseline utility score from the actual QALYs that were measured across 18 months. The analysis will follow the principle of intention-to-treat and will be conducted on each imputed dataset with the point

estimate deriving from the average of 5 datasets and the pooled variance calculated using Rubin's formula.

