To determine the significance of differences, we will perform a two-step gate-keeping test procedure. This will involve first performing an F-test using ANOVA, and then proceeding to do all three pairwise comparisons using two-sided t-test at 5% nominal significance *only if* the F-test has a p-value less than 0.05. With three randomization groups and three pairwise comparisons, this two-step procedure can be shown to preserve the familywise error rate in the strong sense, that is, a false positive comparison will occur at most with 5% probability under all possible scenarios._{3,4} This method is also generally more powerful than Bonferroni's adjustments.

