5.4 Sample Size Determination

The sample size of the trial was determined based on an assumed standard deviation for QALYs of 0.17.5 Additionally, based on a general health-related quality of life outcome in a prior study of management of depression for patients with cancer, we assumed a net improvement in QALYs of 0.155 over 18 months of follow-up for depressed individuals who receive depression treatment in the Screen, Notify and Treat group.6 We assumed a 0.055 gain in QALYs for all patients not directly linked to depression treatment (i.e., those in the No Screen group, the Screen & Notify group and those without elevated depressive symptoms in the Screen, Notify, and Treat group). An important consideration for this trial is that only 20% of patients randomized to the Screen. Notify and Treat group were expected to meet criteria for elevated depressive symptoms and thus, to receive depression treatment. Therefore, assuming an increase in QALYs of 0.21 (0.055 background improvement + net improvement of 0.155) over the 18-month follow-up period for the 20% of patients diagnosed and treated for depression in the Screen, Notify, and Treat group and a 0.055 improvement in QALYs for the 80% of patients in this randomization group without depression, an overall gain in QALYs of 0.086 over the 18 month follow-up period was anticipated in this randomization group (0.21 * 0.2 + 0.055 * 0.8 = 0.086). Thus, we anticipated a difference in QALYs of 0.031 (0.086 change in the Screen. Notify, and Treat group minus 0.055 in the No Screen group or Screen and Notify Group), leading to an expected effect size of 0.18 (= 0.031/0.17). With this effect size, we determined the sample size per group to be 475, which would yield 80% power for a two-sided t-test at 5% level. We chose to determine sample size based on a pairwise comparison at 80% power in the two-step procedure (described above), as a conservative approach relative to powering based on the F-test. Specifically, under the scenario where one group has higher QALY than the other two by an effect size 0.18, the F-test will yield 84% power. Adding in 5% loss to follow-up, we selected an overall sample size of n=500 in each randomization group for an overall sample size of n=1500.

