5.6 Missing Data

CESD-10 questionnaire with missing data will be prorated if that participant answered more than 7 items. The missingness of data will then be assessed using Little's test. If data are found to missing at random, we will perform multivariated imputations to generate 5 imputed datasets by basing on covariates which were predictive of missing pattern such as input from prior visit and site variable; random sampling was used to impute the missing values at baseline. Missing data will be imputed sequentially, starting with the baseline visit, then the 6-month visit, followed by the 12-month and 18-month visits.

In sensitivity analyses, missing data will be handled by carrying the last observed value forward and by using best case-worst case scenario – in best case, we assumed that all missing had perfect health. In worst case scenario, we assumed all missing data had worst health status (QOL = 0).

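### With 5 imputed datasets and no stated seed, a borderline primary result can fall on either side of the p<0.05 gate by chance of the random draw

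*SAP*

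**What the plan says.** SAP 5.6 plans "multivariated imputations to generate 5 imputed datasets". The imputation runs visit by visit: "Missing data will be imputed sequentially, starting with the baseline visit, then the 6-month visit, followed by the 12-month and 18-month visits". For missing baseline values, "random sampling was used to impute the missing values at baseline". SAP 5.3 analyses each completed dataset and pools, with the point "estimate deriving from the average of 5 datasets and the pooled variance calculated using Rubin's formula".

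The test in SAP 5.3 has two steps. A one-way ANOVA F-test across the three arms comes first. Only if its p-value is below 0.05 does the analysis go on to "all three pairwise comparisons using two-sided t-test at 5% nominal significance". The protocol (Statistical Methods, Hypothesis 1) has the same gate and does not mention imputation.

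The only planned missingness figure is the 5% loss to follow-up in SAP 5.4 and in the protocol's Sample Size section. Neither document gives a random seed, a limit on Monte Carlo error, or a rule for raising the number of imputations. The sensitivity analyses in SAP 5.6 (last value carried forward, best case, worst case) vary the missing-data assumption. They do not measure imputation noise.

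**The concern.** Imputed values are random draws, so a pooled result from a finite number of datasets changes when the draws are repeated. Five datasets lose little efficiency, but the p-value can still move enough to matter when it lies close to a fixed threshold.

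Here the threshold is a gate. Hypothesis 1 is a statement about pairwise contrasts, and those are tested only if the F-test passes. For a borderline result, the seed could therefore decide whether the trial's main claim is tested at all. With no seed fixed in advance, two analysts who both follow the SAP could report different answers, and a rerun could change the conclusion.

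**Working it through.** **Inputs from the documents.** Imputations m = 5 (SAP 5.3, 5.6). Gate and pairwise tests at 0.05, two-sided for the pairwise tests (SAP 5.3). SD 0.17, difference 0.031, 475 per group for 80% power, F-test power 84%, 5% loss, 500 per group (SAP 5.4).

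**The plan's own figures first.**
- Normal-approximation n per group: 2 × (1.960 + 0.842)² × (0.17/0.031)² = 472.1, so 473, against the stated 475.
- Pairwise power at 475 per group: 80.2%.
- Inflation for loss: 475/0.95 = 500.
- Noncentral-F power: 82.5% (475 per group, effect size 0.18), 83.5% (475, 0.031/0.17) and 84.5% (500, 0.18), against the stated 84%.

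These agree closely enough to use the design as stated.

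**Assumption: fraction of missing information (FMI).** The documents do not give it. The change in QALYs is built from four correlated visits, so a participant lost late still contributes data, and FMI can be smaller than the fraction lost. It was obtained by simulating 3 × 500 participants with four visits, change-score SD 0.17, between-visit correlation 0.6 and sequential regression imputation with arm in the model:
- 5% loss staggered over visits: FMI about 0.02.
- 5% loss, all before month 6: FMI about 0.036.

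**Formula.** Across seeds the pooled z-statistic has SD of about √(FMI/m). If the converged z is 1.96, its 95% seed range is 1.96 ± 1.96 × √(FMI/m).
- FMI 0.02, m = 5: √(0.02/5) = 0.063; z from 1.836 to 2.084; p from 0.037 to 0.066.
- FMI 0.036, m = 5: √(0.036/5) = 0.085; z from 1.794 to 2.126; p from 0.033 to 0.073 (lower limit 0.0335 before rounding).
- FMI 0.02, m = 50: √(0.02/50) = 0.020; z from 1.921 to 1.999; p from 0.046 to 0.055.

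**The F-test itself.** The gate is a 2-df test, so it was simulated directly. The converged p (1000 imputations) was set to 0.05 and m imputations were redrawn. The five analyses were combined by the multi-parameter version of Rubin's rules, which is an assumption because the SAP does not say how the F-test is pooled. The 95% range of the F-test p over seeds was:

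| Loss pattern | m = 5 | m = 50 |
|---|---|---|
| 5%, staggered | 0.037-0.068 | 0.045-0.055 |
| 5%, all before month 6 | 0.033-0.076 | 0.044-0.057 |

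At 5% staggered loss the SD of p falls from 0.008 to 0.0025. With the between-visit correlation at 0.4 or 0.8, the m = 5 range is 0.039-0.064 or 0.037-0.067. Pairwise t-test p-values behave alike.

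**How close to 0.05 a result must be.** At m = 5, a converged p between 0.039 and 0.063 (FMI 0.02), or between 0.036 and 0.069 (FMI 0.036), has more than a 5% chance of landing on the other side of 0.05.

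**How often it would matter.** Take one pairwise z with mean 2.8 under the design alternative, since 0.031/(0.17 × √(2/475)) = 2.81, or mean 0 under the null. The chance that two seeds disagree on significance is about the density of z at the threshold times the mean gap between two seeds, 2√(FMI/m)/√π.
- Design alternative, FMI 0.02, m = 5: 0.280 × 0.0714 = 2.0%.
- Null, FMI 0.02, m = 5: 2 × 0.0584 × 0.0714 = 0.8%.

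Simulation gave the same, and for both FMI values:

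| Truth | m = 5 | m = 50 |
|---|---|---|
| Design alternative | 2.0-2.7% | 0.6-0.8% |
| Null | 0.8-1.1% | 0.3-0.4% |

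The closed form for the upper design-alternative entry at m = 50 is 0.85%, which is why the rate is given elsewhere as 0.6-0.9%.

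**The case against.** The strongest reply is that 5 imputations are not an error. Rubin's pooled variance, which SAP 5.3 specifies, contains the term for a finite number of imputations. The extra noise is therefore already in the standard error, and nothing here shows bias or an inflated error rate. That stands in full. A reader might infer from the moving p-value that the primary analysis is invalid. The documents do not support this.

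The second reply is that the effect is conditional. Ranges around a converged p of exactly 0.050 are the worst case, and most trials would not end there. A single run with m = 5 differs from its converged answer less often than two runs differ from each other: dividing by √2, about 1.4-1.9% of trials under the design alternative and 0.6-0.8% under the null. This also stands, and it is why the point is limited to borderline results.

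Third, a reader might put 5%, 10% or 20% missing information into the formula and get much wider ranges, up to 0.019-0.117 at 20%. The documents give 5% participant loss, which is a different quantity. Even 20% loss gave 0.028-0.094 in the simulation. The wider figures should not be attached to this plan.

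Last, 50 is a convention, not a derived minimum. At the planned staggered loss, 20 imputations already give 0.043-0.058. That is fair, but it does not argue for staying at 5 when more are free.

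**Conclusion.** The point holds as a minor one about reproducibility. SAP 5.3 and 5.6 combine 5 imputations, no stated seed and a hard gate. At the planned loss, the seed moves an F-test p near 0.05 by roughly 0.015 either way. It would change a pairwise significance call between two runs in about 2-3% of trials under the design alternative and about 1% under the null.

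The size rests on assumptions that the documents do not settle: the mapping from 5% loss to 2-4% missing information, the between-visit correlation, the loss pattern, the content of the imputation model and the way the F-test is pooled. The direction does not depend on them. The exposure grows if missingness exceeds plan: at 20% loss the range of 0.028-0.094 with m = 5 narrows to 0.041-0.061 with m = 50.

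The result does not show a biased estimate, a failure of Rubin's rules, or a primary result that depends on the seed when p is well away from 0.05.

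**What to change.** In SAP 5.3 and 5.6, replace 5 by at least 50 imputed datasets, generated with a seed that is specified in advance and recorded with the analysis. Nothing else in the design, data collection or test procedure needs to change. The cost is computing time and a short edit in the two sections.

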5.4 Sample Size Determination

The sample size of the trial was determined based on an assumed standard deviation for QALYs of 0.17.5 Additionally, based on a general health-related quality of life outcome in a prior study of management of depression for patients with cancer, we assumed a net improvement in QALYs of 0.155 over 18 months of follow-up for depressed individuals who receive depression treatment in the Screen, Notify and Treat group.6 We assumed a 0.055 gain in QALYs for all patients not directly linked to depression treatment (i.e., those in the No Screen group, the Screen & Notify group and those without elevated depressive symptoms in the Screen, Notify, and Treat group). An important consideration for this trial is that only 20% of patients randomized to the Screen. Notify and Treat group were expected to meet criteria for elevated depressive symptoms and thus, to receive depression treatment. Therefore, assuming an increase in QALYs of 0.21 (0.055 background improvement + net improvement of 0.155) over the 18-month follow-up period for the 20% of patients diagnosed and treated for depression in the Screen, Notify, and Treat group and a 0.055 improvement in QALYs for the 80% of patients in this randomization group without depression, an overall gain in QALYs of 0.086 over the 18 month follow-up period was anticipated in this randomization group (0.21 * 0.2 + 0.055 * 0.8 = 0.086). Thus, we anticipated a difference in QALYs of 0.031 (0.086 change in the Screen. Notify, and Treat group minus 0.055 in the No Screen group or Screen and Notify Group), leading to an expected effect size of 0.18 (= 0.031/0.17). With this effect size, we determined the sample size per group to be 475, which would yield 80% power for a two-sided t-test at 5% level. We chose to determine sample size based on a pairwise comparison at 80% power in the two-step procedure (described above), as a conservative approach relative to powering based on the F-test. Specifically, under the scenario where one group has higher QALY than the other two by an effect size 0.18, the F-test will yield 84% power. Adding in 5% loss to follow-up, we selected an overall sample size of n=500 in each randomization group for an overall sample size of n=1500.

5.5 Multiplicity

Our use of the 2-step gatekeeping function will enable us to preserve the familywise error rate in the strong sense, that is, a false positive comparison will occur at most with 5% probability under all possible scenarios._{3,4} This method will enable us to consider multiple group comparisons without using Bonferroni's adjustments.

5.6 Missing Data

CESD-10 questionnaire with missing data will be prorated if that participant answered more than 7 items. The missingness of data will then be assessed using Little's test. If data are found to missing at random, we will perform multivariated imputations to generate 5 imputed datasets by basing on covariates which were predictive of missing pattern such as input from prior visit and site variable; random sampling was used to impute the missing values at baseline. Missing data will be imputed sequentially, starting with the baseline visit, then the 6-month visit, followed by the 12-month and 18-month visits.

In sensitivity analyses, missing data will be handled by carrying the last observed value forward and by using best case-worst case scenario – in best case, we assumed that all missing had perfect health. In worst case scenario, we assumed all missing data had worst health status (QOL = 0).

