In a secondary analysis, we will use a mixed model with a random intercept to assess the change in quality of life utilities over time comparing individuals in the AHA Screen, Notify & Treat group vs. the other two randomization groups. This model will incorporate main effects of time (i.e., baseline, and 6-, 12-, and 18-months post-randomization), treatment group, and the time by treatment group interaction. Using this model, we will be able to calculate the mean utility at each follow-up time period for the 3 groups and determine whether the response profile differs by time across groups.

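### SAP 5.6 lets Little's test decide whether the primary analysis is imputed, gives no primary method for the other result, and does not ensure that randomized arm is in the imputation model

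*SAP*

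**What the plan says.** SAP 5.6 (Missing Data) opens with proration of the CESD-10 and continues: "The missingness of data will then be assessed using Little's test". The next sentence sets the condition: "If data are found to missing at random, we will perform multivariated imputations to generate 5 imputed datasets". No significance level or variable list is given for the test, and no sentence covers the case where the condition fails.

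The imputation model is to use "covariates which were predictive of missing pattern such as input from prior visit and site variable". Randomized arm is not named. The other methods appear only as secondary checks: "In sensitivity analyses, missing data will be handled by carrying the last observed value forward", together with best-case and worst-case filling.

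SAP 5.3 (Primary Efficacy Analysis) says without qualification that the intention-to-treat analysis "will be conducted on each imputed dataset", averaging five datasets and pooling variances by Rubin's formula. The Protocol's Statistical Methods section has no missing-data rule. The only loss rate in either document is in SAP 5.4 and the Protocol's Sample Size section: "Adding in 5% loss to follow-up".

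**The concern.** There are two separate problems.

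**The trigger.** Little's test can reject or fail to reject MCAR. Rejection is compatible with MAR and with missing not at random (MNAR). Non-rejection is compatible with MCAR, with some forms of MNAR, and with mild MAR. The condition in 5.6 can therefore be read two ways:

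- Impute only if the test does not reject. Imputation is then switched off when dropout visibly depends on observed utility, which is the case that imputation under MAR is meant to handle.
- Impute after rejection. This fits the mention of covariates that predict missingness, but then a quiet test leaves no method.

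On either reading one branch has no primary method, and the team would have to choose one after seeing the data.

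**The imputation model.** A covariate enters if it predicts missingness. Arm would qualify only if dropout differed between arms. Yet a model without arm gives lost patients in all arms the same expected follow-up for a given history, which pulls the arm difference toward zero even when dropout is equal. By contrast, the Protocol's secondary mixed model (Hypothesis 1) names "treatment group, and the time by treatment group interaction" and does not depend on a missingness test.

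**Working it through.** **1. The plan's own figures.** From SAP 5.4: difference 0.031, SD 0.17, two-sided 5%, 80% power. n = 2 × (1.960 + 0.842)² × (0.17/0.031)² = 473 per group (485 with the rounded effect size 0.18), against 475 stated. 475/0.95 = 500. The sample size is not in dispute and is the base for what follows.

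**2. Outcome model.** The area under four utilities minus 1.5 × baseline (SAP 5.3) is −1.25·u0 + 0.5·u6 + 0.5·u12 + 0.25·u18. Simulations used 500 per arm, SD of this change 0.17 and a true difference of 0.031. Visit correlations, dropout mechanisms and any loss above 5% are assumptions, because the documents do not give them.

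**3. What Little's test reports** (N = 1500, about 5% loss, correlation 0.6, 5% level, 600 or 1000 datasets per scenario):

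| True mechanism | Rejects |
|---|---|
| MCAR | 4.5–5.5% |
| MAR, per-visit dropout in low vs high prior utility 2.0/1.5%, 2.5/1.0%, 3.0/0.5% | 8%, 61%, 99.5% |
| MAR, log-odds 0.5 or 1.0 per SD of prior utility | 90%, 100% |
| MNAR, dropout depends on the part of the missed score that earlier visits do not predict | 4–6% |
| MNAR, dropout depends on the missed score itself (three gradients) | 27%, 53%, 99% |

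The rates depend on the assumed gradient. The conclusion does not: each result occurs under both MAR and MNAR.

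**4. If imputation is switched off.** Share of the true difference kept when dropout depends on prior-visit utility, in all arms or in one arm:

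- Complete cases: 100–101% at 5% loss, 101–103% at an assumed 20%.
- Last value carried forward: 93–103% at 5%, 72–114% at 20%.

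The near-100% for complete cases is partly a cancellation. At correlation 0.6 the slope of the outcome on u0 is −1.25 + 1.25 × 0.6 = −0.5, while on u6 and on u12 it is +0.2 each. Selection on baseline alone has no such offset. Take per-visit dropout of 3.0% below and 0.5% above the baseline median, in one arm only:

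- Proportion completing: 0.97³ = 0.9127 (low) and 0.995³ = 0.9851 (high), a loss of 5.1%.
- Utility SD: 0.17/√0.85 = 0.184.
- Shift in mean baseline among completers: (0.9851 − 0.9127)/(0.9851 + 0.9127) × 0.798 × 0.184 = 0.0056.
- Shift in outcome: −0.5 × 0.0056 = −0.0028, which is 9% of 0.031.

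Complete cases then keep about 91% or 109%, depending on the arm. The same calculation with 12%/2% per visit (19% loss) gives a shift of 0.0118, or 38%. A separate run gave 90–110% at 5% loss and 61–138% at 20%.

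**5. If arm is left out of the imputation model.** With equal dropout at each interval and 5% in total, 1.7%, 3.4% and 5.0% are missing at 6, 12 and 18 months. If imputed values carried no arm difference at all, the share lost would be (0.5 × 1.7 + 0.5 × 3.4 + 0.25 × 5.0)/1.25 = 3.0%. Observed earlier visits carry part of the effect, so the actual loss is smaller. Forward sequential imputation with five datasets and Rubin pooling gave:

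| Loss by 18 months | Ceiling on shrinkage | Kept without arm | Kept with arm |
|---|---|---|---|
| 5% (planned) | 3.0% | about 97.5% | 99–101% |
| 10% (assumed) | 6.1% | 95–96% | 99–101% |
| 20% (assumed) | 12.4% | 90–91% | 99–101% |

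At 5% loss the shrinkage is about 0.025 × 0.031 = 0.0008 QALY. Even if every lost patient left straight after baseline it could not exceed 0.05 × 0.031 = 0.0016, provided loss is unrelated to benefit. Pairwise power falls from 80.7% to 78.6% at correlation 0.6 (standard error about 1.3 points each). At 20% loss it falls from about 80–81% to 72–73%.

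**The case against.** The strongest reply is that little is at stake. SAP 5.3 can be read as governing, in which case imputation is primary whatever the test shows and there is no gap. The covariate list is introduced by examples, so arm is not excluded. At the only documented loss rate, omitting arm costs 0.0008 QALY, and complete cases keep 100–101% under prior-visit dropout, so it is not obvious that imputation is needed. The 10% and 20% loss rates have no source in the documents. The section also opens with the CESD-10, so one may ask whether it concerns the primary outcome at all.

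Much of this stands. The effect at 5% loss is small, the higher rates are illustrations, and arm is merely not assured. Three parts do not stand:

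- If 5.3 governs, the condition in 5.6 has no function and should go, which is the proposed change. The missing branch and the conflict with 5.3 are one defect seen from two sides.
- The harmlessness of complete cases depends on the dropout pattern. Baseline-dependent dropout in one arm moves the difference by about 9–10% even at 5% loss.
- The five imputed datasets shared with 5.3, and the zero quality-of-life value in the worst-case analysis, show that 5.6 covers the QALY outcome.

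**Conclusion.** The concern holds. SAP 5.6 makes the primary analysis depend on a test that cannot answer the question asked of it, does not say which result counts, and has no primary method for one branch, while 5.3 assumes imputation always happens. That part follows from the null hypothesis of the test and the wording alone and needs no simulation.

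The arm point is weaker: the stated criterion does not ensure inclusion. If arm were omitted, the bias would be toward no difference, about 2.5% of the effect at 5% loss and 9–10% at an assumed 20%. Those sizes rest on visit correlations of 0.4–0.8, monotone dropout and complete baseline data; non-monotone gaps and missing baselines were not examined. This is a repair to pre-specification that should be made. It is not evidence that the trial's result would be materially wrong at the planned loss.

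**What to change.** In SAP 5.6, remove the dependence on Little's test; if the test is wanted, report it descriptively. Then state, in line with 5.3:

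- Missing utilities are assumed missing at random given the variables in the imputation model.
- Multiple imputation under that assumption is the primary method, whatever any test of missingness shows.
- The imputation model includes randomized arm (or imputation is done within arm), site and utilities at prior visits, with further predictors of missingness added as available.

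The zero utility after death in 5.3 and the listed sensitivity analyses need no change on account of this point. The cost is two or three sentences, with the same data, software and sample size.

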3. RANDOMIZATION AND BLINDING

Sequence generation

Participants will be randomly assigned to one of three groups: No Depression Screen, Depression Screen and Notify, or AHA Depression Screen, Notify and Treat. The randomization algorithm will be embedded in the web-based tracking system, using randomly assigned block sizes of 3, 6 and 9.

Concealment Mechanism

Participants will be randomized using the web-based tracking system. "User-roles" are assigned to study personnel, and the randomization tool is only available to unblinded coordinators at each site. Concealment will be ensured as the randomization algorithm will run in the backend, and only the randomization assignment will be visible to the unblinded coordinator after all necessary information about the participant has been entered.

Implementation

All eligible participants who give consent will be randomized by the unblinded coordinator after completion of all baseline assessments. The randomization tool is only available to designated unblinded coordinators (UC) at each site. The UC will enter the required information in the tracking system, after which the participant's group assignment will be immediately available.

If the participant is randomized to the No Depression Screen arm, the UC will inform the participant that no further assessments are required.

If the participant is randomized to the Depression Screen and Notify arm, the UC will administer the PHQ-8. If the PHQ score is ≥ 10, the UC will notify the participant's primary care provider and/or cardiologist either through the tracking system, by email, or mail in accordance with their IRB requirements.

If the participant is randomized to the AHA Depression Screen, Notify, and Treat arm, the UC will administer the PHQ-8. IF the PHQ score is ≥ 10, the UC will inform the patient of the available treatment options. Depending on the participant's choice of treatment, the UC will facilitate the initial contact with the relevant treatment specialist(s), ideally within two weeks of randomization and will work closely with the treatment specialist(s) to monitor the participant's treatment progress. The participant's PCP and/or cardiologist will also be notified of the positive depression screen.

Blinding

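### A missing baseline utility is filled by a random draw that ignores the patient's follow-up, although baseline carries the largest weight in the change-in-QALY endpoint; the imputation model also does not name randomised arm or later visits (minor).

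*SAP*

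**What the plan says.** SAP 5.6 (Missing Data) provides for five imputed datasets, on the condition that the data are found to be missing at random. It makes three statements about the imputation model:

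- Order: "Missing data will be imputed sequentially, starting with the baseline visit, then the 6-month visit, followed by the 12-month and 18-month visits".
- Baseline: "random sampling was used to impute the missing values at baseline".
- Predictors: "covariates which were predictive of missing pattern such as input from prior visit and site variable".

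Neither later visits nor randomised arm is named as a predictor.

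SAP 5.3 (Primary Efficacy Analysis) applies the primary analysis to each imputed dataset, with the "estimate deriving from the average of 5 datasets and the pooled variance calculated using Rubin's formula". The endpoint is the area under the linearly interpolated utility curve over the four assessments, and the change is obtained by "subtracting the QALYs that would have occurred if there was no change in the baseline utility score" from that area. Deaths receive utility 0 afterwards, so they are not imputed.

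Two further statements limit how much can be missing. SAP 3 has participants "randomized by the unblinded coordinator after completion of all baseline assessments", and SAP 5.4 allows for 5% loss to follow-up. Neither document gives an expected rate of missing baseline utilities or of intermittently missed visits.

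**The concern.** Baseline enters the endpoint twice: as the first point of the curve, and as the reference level held constant over 18 months. It is the most influential of the four measurements, yet it is the one the SAP imputes with no information about the patient. Someone with a missing baseline and three observed follow-up utilities receives a baseline unrelated to those utilities. The resulting change score is mostly noise.

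The forward order raises a weaker form of the same issue. A missed 6-month utility is predicted from baseline, and the 12- and 18-month values are not named as predictors even when observed.

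Arm matters separately. If the imputation model omits it, imputed values in all groups are drawn towards a common mean and the estimated difference shrinks. The planned difference is only 0.031 QALY, so there is little room for loss of precision or for shrinkage.

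**Working it through.** **Inputs from the documents.** SD 0.17, difference 0.031, 80% power, two-sided 5%, 475 per group, 5% loss (SAP 5.4); endpoint definition, five imputations and Rubin pooling (SAP 5.3); imputation rules (SAP 5.6).

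**Assumptions (not in the documents).** Between-visit correlations, missingness rates, values missing completely at random, and 0.17 taken as the SD of the change in QALYs.

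**1. The plan's own figure.** n = 2(1.96 + 0.8416)² × 0.17² / 0.031² = 472.1, so 473 per group against 475 stated. Power at 475 is 80.2%, and 475/0.95 = 500. The sample size reproduces.

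**2. Endpoint weights.** With half-year intervals,

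area = 0.25u₀ + 0.5u₆ + 0.5u₁₂ + 0.25u₁₈

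change = area − 1.5u₀ = −1.25u₀ + 0.5u₆ + 0.5u₁₂ + 0.25u₁₈

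**3. Error for one patient with one missing visit.** Take correlations 0.7, 0.6 and 0.5 at lags of 6, 12 and 18 months. The variance of the change is then 0.8625σ², so an SD of 0.17 implies a utility SD of σ = 0.17/√0.8625 = 0.183. A single imputed draw gives an error in the change score of |weight| × σ × √(2(1 − R²)).

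| Missing visit | R², forward only | R², all other visits | Error, forward only | Error, all other visits |
|---|---|---|---|---|
| Baseline | 0 | 0.51 | 0.32 | 0.23 |
| 6 months | 0.49 | 0.62 | 0.092 | 0.079 |
| 12 months | 0.51 | 0.62 | 0.090 | 0.079 |
| 18 months | 0.51 | 0.51 | 0.045 | 0.045 |

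An independent baseline draw also removes the baseline/follow-up covariance. The variance of that patient's change score becomes (1.5625 + 1.2375)σ² = 2.80σ², which is 2.80/0.8625 = 3.2 times the true variance.

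Across exchangeable and AR(1) correlations of 0.5 to 0.8, the error from a drawn baseline is 0.24 to 0.46 (1.4 to 2.7 times 0.17), against 0.21 to 0.24 when later visits are used.

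**4. Effect on the trial.** Simulation with 500 per arm, a true difference of 0.031, five imputations, Rubin pooling and 300 runs per scenario. Arm is in both models. Power is the share of runs with |estimate/SE| above 1.96, and its Monte Carlo error is about 2 to 3 points.

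| Baseline missing | Intermittent, per follow-up visit | Dropout | Correlation | Pooled SE, forward vs all visits | Power, forward vs all visits |
|---|---|---|---|---|---|
| 0% | 0% | 5% | exchangeable 0.65 | 0.0109 vs 0.0109 | 84% vs 84% |
| 0% | 10% | 5% | exchangeable 0.65 | 0.0110 vs 0.0111 | 76% vs 76% |
| 2% | 5% | 5% | exchangeable 0.65 | 0.0114 vs 0.0111 | 79% vs 81% |
| 5% | 5% | 5% | AR(1) 0.8 | 0.0122 vs 0.0112 | 74% vs 82% |
| 10% | 10% | 5% | exchangeable 0.65 | 0.0134 vs 0.0118 | 64% vs 71% |

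With complete baselines the two procedures cannot be told apart. The loss appears only when baselines are missing. It acts mainly through the pooled SE: in the last row the estimates themselves varied between runs by 0.0116 under both procedures. With arm in the model the mean estimate showed no visible bias (0.0307 vs 0.0302 in the last row).

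**5. Arm left out.** In the second row's scenario, omitting arm gave a mean estimate of 0.0274 with forward imputation and 0.0284 with all visits. With arm included the means were 0.0306 and 0.0305, and with complete data 0.0306. The shrinkage therefore occurs under either procedure and is not caused by the forward order.

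**The case against.** Four arguments limit the point, and most of each stands.

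- **Baseline should be nearly complete.** Randomisation follows the baseline assessments, so missing baselines ought to be rare, and at 2% the loss is within simulation error. This stands as an argument about size. It does not remove the issue, because SAP 5.6 itself provides for missing baseline values. The utility also needs seven SF-12 items, and proration is described only for the CESD-10, so a completed interview could still lack a usable utility.
- **The planned missingness is dropout.** Under monotone dropout no later visit exists, and sequential imputation loses nothing. This stands in full for the order of imputation.
- **The predictor list is illustrative.** Its wording does not exclude arm or other visits, and the procedure could be chained equations with the stated order as the visit sequence. This is possible, but an explicit forward order and a separate random-sampling rule for baseline suggest otherwise. The text should settle it.
- **Sensitivity analyses are planned.** SAP 5.6 adds last observation carried forward and best/worst-case analyses. These vary the handling of missing data but do not repair the primary imputation model.

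A reader might infer that the plan discards observed later visits. It does not: under SAP 5.3 every observed utility enters the area under the curve with its full weight. Later visits are only not named as predictors of earlier gaps. A reader might also infer that arm is excluded from the model; the SAP is silent on this.

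**Conclusion.** The point holds as a minor one. The random baseline draw is an inferior rule for the measurement with the largest weight, and the list of imputation predictors is left open where it should be closed.

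For an affected patient, the error in the change score is about 0.32 instead of 0.23. For the trial, the cost is negligible if baselines are essentially complete, about 2 power points at 2% missing (not distinguishable from simulation error) and about 7 to 8 points at 5 to 10% missing. The last range should not be read as the expected loss: the documents give no missing-baseline rate, and the design makes a high one unlikely. The forward order by itself has no material effect. If arm is omitted, the difference shrinks to about 0.027 to 0.028 from 0.031 in the scenario with 10% intermittent missingness per visit and 5% dropout.

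All these sizes rest on assumed correlations and missingness rates, and on values missing completely at random.

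**What to change.** In SAP 5.6, replace the random baseline draw and the sequential rule with a single imputation model, by chained equations or a joint multivariate model. It should contain the utilities at all four visits, randomised arm and site, and should be used for missing baselines as well as for follow-up. State the predictor list in full rather than by example. Report the number and percentage of missing utilities by visit and arm, so that readers can see which row of the table above applies.

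The cost is a change of SAP wording and standard software. No new data are needed, and the endpoint, the pooling and the planned sensitivity analyses stay as they are.
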